Enrolled patients will be prospectively imaged after injection of either the radiotracer Indium-111 Penteotride (OctreoScan) or DOTATATE. We expect imaging 10 patients with OctreoScan and 20 patients with DOTATATE. No one will receive both radiotracer injections.

Patients will be scheduled for imaging Tuesday through Friday (no Mondays), since the dose of OctreoScan and DOTATATE must be requested by noon for next day delivery. Subjects will be advised to remain well hydrated prior to and for at least one day after tracer injection, this to reduce radiation exposure.

Women may participate in this study only if they are certain they are not pregnant. If the subject is a woman of childbearing age, a pregnancy test will be performed before OctreoScan or DOTATATE injection unless she has a history of total hysterectomy, is post-menopausal for more than 2 years or post-tubal ligation for more than 1 year.

OctreoScan Protocol

Visit 1 (Screening)

- Review the study with the subject and obtain written informed consent and HIPAA authorization.
- Assign the subject a unique study number.
- Record demographics data.
- Record medical history, including a history of biopsy-proven systemic sarcoidosis, diagnosis date, and prior treatments.
- Record concomitant medications.
- Schedule subject for Visit 2.

Visit 2 (Study Day 1)

- Subject arrives to the Nuclear Medicine Department.
- Concomitant medications review.
- Perform abbreviated physical examination.
- Perform and record vital signs.
- Place a peripheral intravenous (IV) line.
- Perform STAT quantitative serum hCG testing prior to each administration of Octreoscan
- Administer OctreoScan IV.
- Observe patient for 30 minutes post OctreoScan injection.
- Patient is to have a break and return to the Nuclear Medicine Department in 4 hours.
- Perform first set of images (~90 minutes)
- Subject can leave the Nuclear Medicine Department

[figure not shown]
Visit 3 (Study Day 2)

- Subject returns to the Nuclear Medicine Department 24 hours after OctreoScan injection
- Record any Adverse Experiences.
- Perform second set of images (~90 minutes).
- Subject has completed the study protocol at this point.

Follow Up

• All patients will be contacted by telephone at approximately 36-48 hours following the last scan for AE monitoring.

Figure 3. Example of Study Visits for OctreoScan Protocol

Study Day 1 (Approximately 6 hours)

Study Day 2 (Approximately 2 hours)

24 hours post	Whole Body	SPECT/CT	

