2. Semi-quantitative assessment of OctreoScan cardiac uptake: A heart to blood pool background ratio will be calculated using a circular region of interests (ROI) applied to each focus of increased radiotracer uptake visualized in the left ventricle on the transverse and/or coronal tomographic slice of the fused SPECT/CT images. A background ROI of the same size will be applied to the blood pool in the left ventricular cavity. In addition, the relative myocardial contrast will be assessed with measurement of myocardial uptake in ROIs positioned in: 1) interventricular septum 2) lateral wall 3) anterior wall and 4) inferior wall. ROI placement will be confirmed via image fusion with the CT portion from the SPECT/CT study (similar to Figure 2). This qualitative and semiquantitative approach will be performed in both early and delayed datasets by 2 separate nuclear medicine physicians.

Image Interpretation for DOTATATE:

DOTATATE uptake in the heart will be assessed both qualitative and semi-quantitatively.

1. Qualitative Assessment of OctreoScan cardiac uptake: Two board-certified nuclear medicine physicians will review the limited whole body and cardiac PET/CT images independently of each other and grade each image set based on DOTATATE uptake in the heart as: 1) negative, 2) borderline positive or 3) definitely positive. In this latter case, the number and location (relative to the left ventricular wall position) of positive lesions will be recorded.

2. Quantitative assessment of DOTATATE cardiac uptake: The axial PET image slice with maximum cardiac uptake will be selected. A standardized 15 mm circular region will be placed over each myocardial wall area with the peak activity. ROI placement will be confirmed via image fusion with the CT portion from the PET/CT study. Each ROI will be used to derive maximum (SUVmax) and mean standardized uptake values (SUVmean). A background ROI of the same size will be applied to the blood pool in the left ventricular cavity, and similarly, SUVmax and SUVmean will be derived to serve as reference. Then, signal-to-background ratios will be calculated.

This qualitative and semi-quantitative approach will be performed in both early and delayed datasets by 2 separate nuclear medicine physicians.

BIOSTATISTICAL ANALYSIS

a. Specific data variables being collected for the study

Please see excel attachments

b. Study endpoints

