Primary Endpoint: Positive or abnormal OctreoScan or DOTATATE uptake in patients with cardiac sarcoidosis

Secondary Endpoint: Differences in OctreoScan uptake at 4 hours vs. 24 hours post-radiotracer injection

c. Statistical methods

Data Ascertainment and Analysis:

All statistical analysis will be done using SPSS (version 21.0). A P value <0.05 will be considered statistically significant for all calculations.

Qualitative assessment of OctreoScan or DOTATATE cardiac uptake: First, Cohen's kappa coefficient will be used to examine the visual inter-rater agreement between readers. We expect a kappa of at least 0.9 (excellent). Subsequently, the percentage of patients with abnormal OctreoScan or DOTATATE will be compared between patients with suspected sarcoidosis and those in a control group (Table 1, Figure 2) using chi2.

Semiquantitative assessment of OctreoScan or DOTATATE cardiac uptake: The heart-to-blood pool ratio is a unitless continuous variable. We will use paired t-test to compare within group OctreoScan uptake between early and delayed imaging, and independent-measures t test to compare OctreoScan or DOTATATE uptake between patients with suspected sarcoidosis and the control group.

We will also investigate whether delayed imaging may lead to improved lesion detection performance due to a higher/better target-to-background ratio compared to early imaging. We will employ chi2 to compare if percentage of patients with abnormal OctreoScan varies significantly both on a patient- and lesion-basis between early and delayed imaging in both study groups.

Evaluation of early vs. delay imaging: We will employ chi2 to compare if percentage of patients with abnormal OctreoScan varies significantly both on a patient- as well as lesion-basis between early and delayed imaging in both study groups.

Comparison with FDG-PET: We will also compare if foci of increased OctreoScan or DOTATATE uptake are similar in number and localization compared to FDG-PET scans.

Expected Results:

Our main hypothesis is that OctreoScan or DOTATATE uptake in the heart will be semiquantitatively (heart-to blood pool ratio will be ≥ 2.0) high enough to allow visualization of OctreoScan or DOTATATE activity in patients with cardiac sarcoidosis, compared to the control group, where myocardial uptake will be similar to blood pool activity (heart-to blood pool ratio of ~ 1.0).

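### The OctreoScan patient-versus-control t test does not say which heart-to-blood-pool ratio it uses; if it is the focus ratio, sites chosen for high uptake are compared with unselected control walls.

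*Combined protocol and SAP*

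**What the plan says.** Biostatistical Analysis, c, introduces the semiquantitative variable with "The heart-to-blood pool ratio is a unitless continuous variable" and plans an "independent-measures t test to compare OctreoScan or DOTATATE uptake between patients with suspected sarcoidosis and the control group". It names no region of interest (ROI), time point or per-patient summary. The sentence does not identify the control group; the preceding chi2 sentence points to Table 1 and Figure 2, and no other control group is described.

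Section V.d defines two OctreoScan measures in patients:
- The heart-to-blood-pool ratio, from an ROI "applied to each focus of increased radiotracer uptake visualized in the left ventricle". A patient can have none, one or several of these.
- Four fixed walls (septum, lateral, anterior, inferior), introduced with "In addition, the relative myocardial contrast will be assessed with measurement of myocardial uptake in ROIs positioned in".

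The 15 controls (section I.c and Table 1) were scanned at 24 hours at another centre. They were measured with ROIs of about 20 mm on the same four walls and summarised as 0.94 ± 0.17. No focus-based value is reported for them.

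For the list of variables, Biostatistical Analysis, a, says only "Please see excel attachments"; those attachments are not part of the public document. On numbers, section V.a says "We expect imaging 10 patients with OctreoScan and 20 patients with DOTATATE".

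**The concern.** Two readings of the t test are open.

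1. **The focus ratio is tested.** It is the patient measure that carries the name used in the statistical section, so this is the more natural reading. Patient values then come from sites picked because they look hot, and control values from sites fixed in advance. That selection raises the patient mean even where the tissue does not differ. A patient without a visible focus has no focus ratio. If such patients drop out, the mean difference no longer reflects how many patients show uptake.
2. **The four-wall values are tested.** The selection mismatch disappears. However, the protocol plans those walls as a measure of relative contrast, and the statistical section does not name them.

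At stake are the estimated difference and the P value of one supporting test. The ratio is also the quantity in Aim 1 and in the main hypothesis, so readers will look at that estimate.

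**Working it through.** **Inputs.** Table 1 wall means and SDs: septum 1.02 and 0.15, inferior 1.03 and 0.13, lateral 0.92 and 0.15, anterior 0.81 and 0.15; n = 15 controls. Ten OctreoScan patients (section V.a). Hypothesised patient ratio 2.0 (Aim 1). The correlation between walls within a person is not given, so it is varied from 0 to 0.9 (assumption).

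**1. Reproducing the control figure.**
- Mean = (1.02 + 1.03 + 0.92 + 0.81)/4 = 0.945, against the printed 0.94.
- SD of 60 pooled wall values (15 people × 4 walls) = sqrt[(14 × sum of SD² + 15 × sum of (wall mean − 0.945)²)/59] = sqrt[(14 × 0.0844 + 15 × 0.0317)/59] = 0.168, against the printed 0.17.

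The control summary therefore behaves as a pool of fixed-wall values.

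**2. Can 0.17 be a between-person SD?** The SD of a per-person four-wall mean is largest at wall correlation 1, where it equals the average wall SD: (0.15 + 0.13 + 0.15 + 0.15)/4 = 0.145. With each SD at its rounding limit it is (0.155 + 0.135 + 0.155 + 0.155)/4 = 0.15. A printed 0.17 means at least 0.165. So it is not the SD of 15 per-person four-wall means. At correlations 0 to 0.9 that SD would be 0.073 to 0.139.

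**3. Illustration of the selection component.** Give patients and controls identical myocardium (multivariate normal, Table 1 values). Take the hottest of four walls in patients, as a rough stand-in for a chosen site, and the four-wall mean in controls.

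| Wall correlation | Mean of hottest wall | Minus 0.945 |
|---|---|---|
| 0 | 1.124 | 0.18 |
| 0.3 | 1.104 | 0.16 |
| 0.5 | 1.089 | 0.14 |
| 0.7 | 1.073 | 0.13 |
| 0.9 | 1.052 | 0.11 |

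With the same rule in both groups, a 10-versus-15 t test rejects in about 5% of simulated trials. No simulated hottest wall reached 2.0 (highest value 1.83).

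**4. Illustration of leaving out patients without a focus.** Assume that such patients are dropped and that every focus reads 2.0. The difference is then 2.0 − 0.945 = 1.055, about 1.06, whether 3, 5 or 8 of 10 patients have a focus. Now use one value for all 10 patients, with one randomly placed wall at 2.0 in each focus patient and control-like values elsewhere.

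| Patients with a focus | Focus ratio, others dropped | Highest wall, everyone | Four-wall mean, everyone |
|---|---|---|---|
| 3 of 10 | 1.06 | 0.26 to 0.29 | 0.08 |
| 5 of 10 | 1.06 | 0.44 to 0.47 | 0.13 |
| 8 of 10 | 1.06 | 0.70 to 0.76 | 0.21 |

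The last column is the proportion with a focus × 1.055/4; for example, 0.3 × 0.264 = 0.08.

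**The case against.** **The four-wall reading may be the intended one.** The controls' four walls are already planned in every OctreoScan patient, with placement likened to Figure 2, and the unseen attachments may define the variable. This stands as a possibility, and on that reading there is no selection mismatch. The likeness to Figure 2 concerns ROI placement, though, and does not say which value is tested.

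**A reader might infer that the t test has a very high false-positive rate.** In the step 3 setting, P < 0.05 occurs in 44% (correlation 0.9) to 99.8% (correlation 0) of simulated trials. These are not rates for this trial. They test a hottest-wall rule that the plan never states. A focus ratio exists only where a focus is seen; control myocardium looked the same as blood pool, and the highest control wall value was 1.33. In the simulation only 2% to 3% of hottest walls exceed 1.33, so control-like hearts would rarely yield a focus ratio at all.

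**A reader might also infer that the net result must favour patients.** The documents do not support that. Controls came from another centre with scatter handling not stated, while patient images are scatter-corrected. Section I.c attributes the higher inferior and septal control values mostly to scatter. If correction lowered those two walls in patients to the lateral/anterior average, (0.92 + 0.81)/2 = 0.865 (an assumption), the step 3 gap would fall to between −0.01 and +0.08.

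**Step 4 follows from its assumptions.** That is correct: the plan does not say that patients without a focus are dropped, or that each focus reads 2.0. The step shows only what the focus ratio cannot convey if they are.

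**Table 1 does not define its Total LV row.** Also correct. The bound in step 2 applies to a per-person four-wall mean, and the match to 60 pooled values is strong but indirect evidence.

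**Conclusion.** The point holds as a conditional one. The t test does not identify its value. On its most natural reading it compares sites chosen for high uptake with unselected sites and gives patients without a focus no value. The selection component inflates the difference; 0.11 to 0.18 illustrates its order of magnitude under Table 1 values, normality and assumed wall correlations. The net size and direction cannot be derived from the documents. If the four-wall values are meant, the problem does not arise.

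The finding does not reach the 2.0 level in Aim 1, the chi2 comparison, or the listed endpoints, of which the primary is "Positive or abnormal OctreoScan or DOTATATE uptake in patients with cardiac sarcoidosis". All patients must already show abnormal FDG uptake, so a true difference is plausible and the main risk is to its estimated size.

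The 20 planned DOTATATE patients are outside this point. Their ROI rule, "A standardized 15 mm circular region will be placed over each myocardial wall area with the peak activity", is itself open to more than one reading, and comparing another tracer with OctreoScan controls is a separate question.

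Severity: minor to moderate.

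**What to change.** In Biostatistical Analysis, c, state that:
- the OctreoScan t test uses one value per person, computed by the same rule in patients and controls from the four named-wall ratios at 24 hours (the controls' time point), for every patient whether or not a focus is seen;
- either the four-wall mean or the highest wall is the main value, chosen in advance, with the other as a sensitivity analysis;
- focus ratios are reported descriptively;
- control values and their SD are computed from the 15 individual records, and 0.17 is not used as a between-person SD.

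**Cost.** The edit is short and needs no new scans, since the wall ROIs are already planned in patients. It assumes that the individual control wall values were kept. A single value per person also needs a rule for combining the two patient readings; the account of the controls does not say how many readers measured them, so matching on that point may not be possible.

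**Trade-off between the two values.** The mean dilutes focal uptake: one wall at 2.0 moves it by only 0.24 to 0.30, depending on the wall. The highest wall keeps focal uptake, but in control-like hearts it is the septum or inferior wall in 80% to 98% of cases, which are the walls section I.c links to scatter, and it raises the control reference from 0.94 to about 1.05 to 1.12. Either choice is defensible if it is fixed beforehand and applied to both groups.

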patients (7 men and 8 women, mean age 62 years) who underwent OctreoScan with SPECT/CT of the chest for a clinical indication between the periods of April and November of 2013 at the University of Washington in Seattle. Most common clinical indication was detection of local and/or metastatic neuroendocrine tumors. Patients were injected with ~ 6 mCi of OctreoScan, and SPECT/CT of the chest was acquired 24 hr post-injection. OctreoScan uptake was semiquantitatively calculated using a target to blood pool ratio approach. Figure 2 depicts fused SPECT/CT images of how this was performed. Circular region of interests (ROI) of ~20 mm diameter were applied to left ventricular (LV) cavity blood pool (used as background, 2A and 2D), LV anterior (2B), inferior (2C), lateral wall (2E) and septum (2F), as well as the lungs (not shown), liver (2G), spleen (2G) and kidneys (2H). Results: Visually, the myocardium exhibited indistinguishable activity compared to the LV blood pool. However, there was significant LV regional differences in the uptake ratio/index as shown in **Table 1**. The inferior wall and septum showed higher (above blood pool) and the lateral and anterior walls lower (below blood pool) uptake ratios. This is most likely due to scatter emitted from the liver and spleen (Fig 2G) into the inferior wall (Fig 2C) and, to a lesser extent, the inferior portion of the septum. Likewise, identification of the septal wall (Fig 2F) was difficult given the lack of enough contrast definition on SPECT and CT images, for which an anatomical assumption was made, which makes ROI-based estimates less accurate at this location. These data demonstrated that under baseline conditions. OctreoScan uptake in the heart is indistinguishable from LV blood pool (~ 0.94 ± 0.17). These findings provide solid empirical basis for the work proposed in this project; the hypotheses are mechanistically plausible, clinically important, and testable.

d. Differences between OctreoScan and DOTATATE

There are important biological, technical, and practical differences between these radiopharmaceuticals that deserve a brief mention. Like indium-111 pentetrotide (Octreoscan®), 68-gallium dotatate has similar affinity for the same group of somatostatin receptors in inflammatory leukocytes (preferentially somatostatin receptor 2). The availability of 68-gallium dotatate provides several advantages, which are highly beneficial to the patients in this pilot study, including:

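### Read literally, the DOTATATE rule takes every ratio from one axial slice, so foci or walls off that slice get no ratio and values need not match the four-wall controls or the follow-up scan

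*Combined protocol and SAP*

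**What the plan says.** Section V.d, Image Interpretation for DOTATATE, item 2, starts with slice selection: "The axial PET image slice with maximum cardiac uptake will be selected". It continues: "A standardized 15 mm circular region will be placed over each myocardial wall area with the peak activity". SUVmax and SUVmean are taken from each ROI and from a blood-pool ROI of the same size in the left ventricular (LV) cavity. The rule ends: "Then, signal-to-background ratios will be calculated". No other slice or orientation is mentioned, and nothing says which ratio represents the patient.

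The OctreoScan rule in the same section is broader. Its ROI is "applied to each focus of increased radiotracer uptake visualized in the left ventricle on the transverse and/or coronal tomographic slice", and it adds "ROIs positioned in: 1) interventricular septum 2) lateral wall 3) anterior wall and 4) inferior wall".

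The control series (Section I.c, Table 1 and Figure 2) has ROIs in the same four walls and reports a total LV ratio of 0.94 (SD 0.17).

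The DOTATATE visual read is separate and uses the whole cardiac PET/CT. For definitely positive scans, "the number and location (relative to the left ventricular wall position) of positive lesions will be recorded".

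The Biostatistical Analysis section plans an independent t test of OctreoScan or DOTATATE uptake against the control group. Sub-Aim 3 explores the effect of treatment on DOTATATE activity at follow-up.

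**The concern.** The left ventricle lies obliquely in the chest, so one body-axial slice need not contain all four walls or all foci. A patient with two lesions on the visual read may have a ratio for only one of them.

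Three uses of the DOTATATE ratio are exposed:

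- **t test against controls.** The control value is a four-wall value. The DOTATATE rule guarantees only whatever the hottest slice contains.
- **Comparability between tracers.** OctreoScan patients have per-focus and four-wall ratios. DOTATATE patients may not.
- **Sub-Aim 3.** The hottest slice is chosen afresh on each scan, and no rule ties follow-up ROIs to baseline locations. If the hottest focus responds and another does not, the follow-up measurement can move to a site with no baseline ratio.

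**Working it through.** The documents give no number, size or position of foci and no heart orientation, so there is no stated rate to reproduce. The only figure of the plan's own that bears on the point is the control value.

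**1. Control value.** Table 1 gives septum 1.02, inferior 1.03, lateral 0.92 and anterior 0.81.

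(1.02 + 1.03 + 0.92 + 0.81) / 4 = 3.78 / 4 = 0.945

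This agrees with the reported 0.94 to rounding, so the control figure behaves as a four-wall mean.

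**2. How the summary depends on the slice (illustrative values).** Take one wall at 3.0 and three unaffected walls at about 1.0.

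- Peak: 3.0, whatever else is on the slice.
- Mean with four walls on the slice: (3.0 + 1.0 + 1.0 + 1.0) / 4 = 1.5.
- With three: (3.0 + 1.0 + 1.0) / 3 = 1.67.
- With two: (3.0 + 1.0) / 2 = 2.0.

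The peak does not move. An average of on-slice walls runs from 1.5 to 2.0 according to anatomy alone, and only the first is built like the control value. The plan does not say which summary is used.

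**3. Follow-up (illustrative values).** At baseline, focus A is 3.0 and focus B, off A's slice, is 2.2. Under treatment A resolves and B stays at 2.2. The follow-up slice moves to B.

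Change in slice-based peak = (3.0 − 2.2) / 3.0 = 0.8 / 3.0 = 27% fall

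Per-focus ratios would show one focus resolved and one with 0% change. The literal rule leaves B without a baseline ratio.

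**4. How often a second focus is off the slice (assumed geometry).** Assume the slice passes through the centre of the hottest focus, and that focus centres are independent and uniform over an LV axial height H. A second focus of axial extent L is cut by the slice with probability 1 − (1 − L/(2H))², so it is missed with probability (1 − L/(2H))².

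| L | Missed, H = 70 mm | Missed, H = 100 mm |
|---|---|---|
| 10 mm | 86% | 90% |
| 20 mm | 73% | 81% |
| 40 mm | 51% | 64% |
| 60 mm | 33% | 49% |

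The probability equals one half at L = 2H(1 − √0.5) = 0.586H, which is 41 mm at H = 70 and 59 mm at H = 100. Above that extent a majority is no longer missed.

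A second model places 20 mm foci at random on a half-ellipsoid 80 mm long with radius 28 mm, more than 20 mm apart. The second focus is off-slice in 74%, 77% and 79% of cases at caudal tilts of 20, 35 and 50 degrees.

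**5. How often a wall is off the slice (assumed geometry).** The model is a half-ellipsoid shell, length 70 or 85 mm and radius 25 or 30 mm, divided into four equal sectors. The slice is set at the height of a random surface point. A wall counts as present if it supplies at least 2% of the surface points in the slice.

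| Tilt of long axis from axial plane | At least one wall absent |
|---|---|
| 20° | 77% to 96% |
| 40° | 36% to 51% |
| 60° | 15% to 25% |

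The rate is governed by tilt, which the documents do not give.

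**The case against.** The strongest reply is that the plan's main analyses survive. The primary endpoint is positive or abnormal uptake, and the visual read is not confined to one slice. The main hypothesis of a ratio of at least 2.0 can be tested on the patient's maximum, which the hottest slice keeps. No per-focus or per-wall DOTATATE test is specified, and the lesion-level chi-squared test covers OctreoScan only. All of this stands.

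Four stronger readings are tempting, and the documents do not support them:

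- **That the rule contradicts itself by requiring every wall.** The text qualifies each wall area by its peak activity. This may mean only the hot areas on the chosen slice, in which case the two sentences agree. It is an ambiguity, and either reading needs clearer wording.
- **That most additional foci, and often whole walls, are lost.** The documents give no rate. The results above depend on assumed focus size and tilt, and patients with one focus lose no focus.
- **That the FDG comparison in Sub-Aim 2 is damaged.** It uses number and localization of foci, which come from the visual read.
- **That total cardiac activity is understated most in widespread disease.** The protocol defines no such measure, and extensive uptake is more likely to cross the slice.

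The data variables are listed in attachments that are not available here, so per-wall DOTATATE fields may exist. They would not change the written slice rule.

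What remains is that the stated rule produces ratios not built like the control or OctreoScan ratios, and that nothing anchors measurement at follow-up.

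**Conclusion.** The point holds in a limited form. As written, off-slice foci and walls get no DOTATATE ratio, in the tracer group that makes up 20 of 30 planned patients. This affects the like-for-like t test against the four-wall controls, comparability between tracers, and Sub-Aim 3. It does not affect the peak ratio, the visual endpoint or Sub-Aim 2.

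The 27% fall in the follow-up example is an illustration, not an estimate. Frequencies rest wholly on assumed geometry: about 73% to 81% of second 20 mm foci missed, no longer a majority once extent exceeds about 41 to 59 mm, and at least one wall absent in about 15% to 96% of cases as tilt goes from 60 down to 20 degrees. How many patients have more than one focus is unknown.

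This should be changed because the change is cheap and the rule is already stated for the other tracer. It does not threaten the primary endpoint.

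**What to change.** Replace the first two sentences of the DOTATATE quantitative rule with:

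> For every focus recorded on the visual read, and for each of the four left ventricular walls (septum, lateral, anterior, inferior), a 15 mm ROI is placed on the transverse and/or coronal slice where that focus or wall has its peak activity; one blood-pool ROI is placed per scan in the LV cavity.

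Then state in Statistical methods that:

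- the four-wall mean ratio, using SUVmean, enters the t test against the four-wall control values;
- the hottest ratio is reported as the patient-level peak for the hypothesis of at least 2.0;
- follow-up ROIs are placed at the baseline locations as well as at any new focus.

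The cost is a few more ROIs per scan by the same two readers on images already acquired. No new scan or patient is needed. The change does not remove every difference from the controls, who were imaged with OctreoScan using ROIs of about 20 mm.

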- a. higher contrast and spatial resolution of PET/CT for detection of small lesions, which we think will result in improved sensitivity as compared to indium-111 pentetrotide SPECT;
- b. a nearly 75% reduction in the whole body effective radiation dose to patients from a single administration of gallium-68 dotatate (from 16.4 mSv for Octreoscan to 4.3 with Dotatate);
- c. convenience for patients and practical to perform. The entire gallium-68 dotatate PET imaging procedure takes ~2 hours in a single visit, compared to ~24 hours over 2 visits for octreoscan imaging.

II. SPECIFIC AIMS

Aim 1

To investigate if patients with clinically suspected cardiac sarcoidosis exhibit a myocardial OctreoScan or DOTATATE signal high enough (heart-to-blood pool ratio ≥ 2.0) to be visually detected compared to a control group of individuals (expected heart-to-blood pool ratio of ~ 1.0).

Sub-Aim1

To evaluate whether 4-hour (early) compared to 24-hour (delayed) post-OctreoScan injection imaging yields similar lesion detection performance.

Sub-Aim2

To correlate localization and number of increased radiotracer foci between FDG-PET and OctreoScan or between FDG-PET and DOTATATE studies.

Sub-Aim3

To explore the effect of treatment on DOTATATE activity in the heart on follow-up scans

III. SUBJECT SELECTION

We will enroll 30 adult subjects meeting the following inclusion/exclusion criteria.

a. Inclusion Criteria for initial study

- Individuals aged 18 or older

- Documentation of biopsy-proven sarcoidosis OR patients with typical findings on FDG PET and MRI without previous biopsy.

- Clinical suspicion of cardiac involvement defined as the presence of any of the following: high-degree A-V nodal block, complete bundle branch block, reduced left or right ventricular systolic function, any cardiac arrhythmia, and/or unexplained chest pain, dyspnea or syncope

- PET/CT imaging demonstrating abnormal myocardial FDG uptake consistent with active inflammatory myocardium.

b. Exclusion Criteria for initial study

-Initiation of steroids or any other immunosuppressive medication(s) following the completion of FDG-PET, as these medications, in theory, may subsequently suppress OctreoScan or DOTATATE uptake in the heart.

- Patients with history of neuroendocrine tumors (specially insulinomas)
- Patients taking the medication Octreotide
- Patients on total parenteral nutrition (TPN)
- Women who are pregnant or breastfeeding

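### The visual test of the primary endpoint compares patients with a control series that appears to have no positives, so P<0.05 shows only that positivity exceeds about zero

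*Combined protocol and SAP*

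**What the plan says.** Under Biostatistical Analysis, b. Study endpoints, the primary endpoint is "Positive or abnormal OctreoScan or DOTATATE uptake in patients with cardiac sarcoidosis". It is a yes/no outcome with no target rate.

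Under c. Statistical methods, after the kappa analysis of reader agreement, "the percentage of patients with abnormal OctreoScan or DOTATATE will be compared between patients with suspected sarcoidosis and those in a control group". The comparator and test are given as "those in a control group (Table 1, Figure 2) using chi2", and "A P value <0.05 will be considered statistically significant for all calculations". The other planned chi-square tests concern early against delayed OctreoScan imaging, which is the secondary endpoint.

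The control series is described in I.c Study Rationale: 15 consecutive adults scanned with OctreoScan for clinical reasons. Its visual result is already known: "Visually, the myocardium exhibited indistinguishable activity compared to the LV blood pool".

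On the patient side, III. Subject Selection says "We will enroll 30 adult subjects meeting the following inclusion/exclusion criteria", and one of those inclusion criteria is an FDG PET/CT showing abnormal myocardial uptake. Section V.a adds "We expect imaging 10 patients with OctreoScan and 20 patients with DOTATATE".

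Two other statements bear on the point. Aim 1 asks whether the myocardial signal is high enough to be seen, compared with controls. The Expected Results text hypothesizes that, counted by patient, the tracers will find about as many abnormal cases as FDG-PET. No test, margin or interval is attached to that hypothesis.

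**The concern.** A two-group test is informative when the control rate is uncertain or is a meaningful benchmark. Here the control result was known before the study and is close to zero. The test then reduces to asking whether positivity in the patients is distinguishable from almost none. For patients who all enter with abnormal myocardial FDG uptake, that is a low bar.

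Aim 1 and the FDG hypothesis ask something more demanding: in what share of these patients is the signal visible? The plan provides no confidence interval for that share and no rate to read it against. The only inferential statement attached to the primary endpoint could therefore be a small P value while most patients have negative scans.

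**Working it through.** The plan gives no power or precision calculation for the 30 patients, so there is no figure to reproduce. The check is to find the smallest number of positive patients that makes the planned test significant.

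**Inputs from the documents**
- Patients: 30 in total (III. Subject Selection), expected as 20 DOTATATE and 10 OctreoScan (V.a).
- Controls: 15 (I.c, Table 1).
- Threshold: P<0.05, taken as two-sided. The plan does not state sidedness or whether a continuity correction applies.

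**Assumption**
- Controls positive: 0/15, inferred from the general visual description. One positive control (1/15) is shown as a sensitivity case.

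**Formula.** For x of n patients positive and 0 of 15 controls positive, the uncorrected Pearson statistic is

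X² = N(15x)² / [n × 15 × x × (N − x)], with N = n + 15 and a critical value of 3.84.

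- x = 7, n = 30: 45 × 105² / (30 × 15 × 7 × 38) = 4.14, P = 0.042.
- x = 6, n = 30: 45 × 90² / (30 × 15 × 6 × 39) = 3.46, P = 0.063.

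So 7 of 30 is the smallest significant count by Pearson. With 7 positives the smallest expected count is 7 × 15/45 = 2.33, which is low for chi-square, so Fisher and Yates are shown as well.

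**Smallest count of positive patients giving P<0.05**

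| Patients | Controls positive | Pearson | Fisher | Yates | Patients with a negative scan |
|---|---|---|---|---|---|
| Pooled, 30 | 0/15 | 7 (P=0.042) | 8 (P=0.038) | 9 (P=0.048) | 70–77% |
| DOTATATE, 20 | 0/15 | 5 (P=0.037) | 6 (P=0.027) | 7 (P=0.033) | 65–75% |
| OctreoScan, 10 | 0/15 | 3 (P=0.024) | 4 (P=0.017) | 4 (P=0.034) | 60–70% |
| Pooled, 30 | 1/15 | 10 (P=0.0497) | 11 (P=0.038) | 12 (P=0.048) | 60–67% |

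The last column is 1 − x/n; for example 1 − 7/30 = 77% and 1 − 12/30 = 60%.

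**How often this would happen.** With 0/15 controls, the chance of significance in 30 patients is the binomial probability of reaching the threshold count.

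| True positivity | Pearson (≥7) | Fisher (≥8) | Yates (≥9) |
|---|---|---|---|
| 25% | 65% | 49% | 33% |
| 30% | 84% | 72% | 57% |

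With one positive control the Pearson threshold is 10, and the chance at a true 30% falls to 41%.

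**What an interval would show instead** (exact Clopper-Pearson 95%)
- 7/30 = 23%: 9.9% to 42.3%.
- 5/20 = 25%: 8.7% to 49.1%.
- 3/10 = 30%: 6.7% to 65.2%.
- For contrast, 24/30 = 80%: 61.4% to 92.3%.

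The first three results are all significant by Pearson against 0/15, but none is close to the FDG rate of 100% that the inclusion criterion guarantees.

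**The case against.** Five points can be made for the plan.

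**No success rule is stated.** A reader might infer that the plan would declare a tracer successful at 7/30. The documents do not support that. They define statistical significance, not success, and do not label this chi-square the primary comparison. The main hypothesis is also tied to a heart-to-blood-pool ratio of at least 2.0, with a separate t test against controls. This objection stands. The remaining problem is narrower: this is the only test planned for the binary primary endpoint, and the t test sets no required share of patients.

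**The FDG hypothesis is a safeguard.** A tracer positive in 7 of 30 would visibly contradict the expectation of a similar number of abnormal cases to FDG-PET, and a comparison of foci is planned. That helps a careful reader, but neither comparison has a test, margin or interval.

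**0/15 is inferred.** Correct. No three-level grades are reported for the controls, and the plan does not say whether borderline positive counts as abnormal. One positive control moves the pooled threshold to 10–12 of 30. The size changes; the conclusion does not.

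**FDG positivity is not proof of disease.** The background section calls FDG-PET non-specific for cardiac sarcoidosis, so a negative scan here is not necessarily a missed case. The figures are therefore negative scans among FDG-positive patients. The protocol does call FDG PET the reference modality in VIII.b.

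**It is a pilot, and Aim 1 asks for a comparison with controls.** Both are true, which is why the comparison should stay. They do not explain the absence of an estimate with an interval, the natural analysis for a pilot.

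**Conclusion.** The concern holds in this form. Under 0/15 controls, the planned test is significant from 7/30 (Pearson), 8/30 (Fisher) or 9/30 (Yates). With one positive control it is significant from 10–12 of 30. Significance is thus compatible with 60% to 77% of FDG-positive patients having a negative scan. A significant P would support the statement that positivity is not absent. It would not support reliable visibility or similarity to FDG-PET.

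These percentages describe observed counts. It would be too strong to say that a tracer truly negative in three quarters of patients is bound to be significant: at a true 25% the chance is 33% to 65%, depending on the test. The choice between chi-square and Fisher is not the issue, since the pooled threshold moves by only one patient. The data remain usable; what needs changing is the inference planned from them.

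**What to change.** In Statistical methods, make the main result for the primary endpoint, separately for each tracer, the proportion of enrolled FDG-positive patients with an abnormal scan and its exact 95% confidence interval. Read it explicitly against the Expected Results hypothesis about FDG-PET. State before the reads whether borderline positive counts as abnormal, because the proportion depends on it.

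Keep the control comparison as supportive, with a sentence saying that P<0.05 shows only that positivity is not absent.

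A minimum rate fixed before the reads is optional and for the sponsor to choose. It has a real cost in groups this small. For example, requiring a lower limit above 50% means 9/10 for OctreoScan or 15/20 for DOTATATE; at a true rate of 80% these are reached 38% and 80% of the time.

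The change needs about a paragraph of text and no new patients or scans. The downside is wide intervals, especially with 10 OctreoScan patients (8/10 would give 44% to 98%), and a less favourable headline than a P value below 0.05.
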